5.3 TOXICITY CRITERIA

The following adverse event management guidelines are intended to ensure the safety of each patient while on the study. The descriptions and grading scales found in the revised NCI Common Terminology Criteria for Adverse Events (CTCAE) version 4.0 will be utilized for AE reporting. All appropriate treatment areas should have access to a copy of the CTCAE version 4.0. A copy of the CTCAE version 4.0 can be downloaded from the CTEP web site (http://ctep.cancer.gov/protocolDevelopment/electronic_applications/ctc.htm#ctc_40).

6.0 SAFETY REPORTING REQUIREMENTS/DATA AND SAFETY MONITORING PLAN

6.1 DEFINITIONS

6.1.1 Adverse Event

Any untoward medical occurrence in a human subject, including any abnormal sign (for example, abnormal physical exam or laboratory finding), symptom, or disease, temporally associated with the subject's participation in research, whether or not considered related to the subject's participation in the research.

6.1.2 Suspected adverse reaction

Suspected adverse reaction means any adverse event for which there is a reasonable possibility that the drug caused the adverse event. For the purposes of IND safety reporting, 'reasonable possibility' means there is evidence to suggest a causal relationship between the drug and the adverse event. A suspected adverse reaction implies a lesser degree of certainty about causality than adverse reaction, which means any adverse event caused by a drug.

6.1.3 Unexpected adverse reaction

An adverse event or suspected adverse reaction is considered “unexpected” if it is not listed in the investigator brochure or is not listed at the specificity or severity that has been observed; or, if an investigator brochure is not required or available, is not consistent with the risk information described in the general investigational plan or elsewhere in the current application. “Unexpected” also refers to adverse events or suspected adverse reactions that are mentioned in the investigator brochure as occurring with a class of drugs or as anticipated from the pharmacological properties of the drug, but are not specifically mentioned as occurring with the particular drug under investigation.

6.1.4 Serious

An Unanticipated Problem or Protocol Deviation is serious if it meets the definition of a Serious Adverse Event or if it compromises the safety, welfare or rights of subjects or others.

6.1.5 Serious Adverse Event

An adverse event or suspected adverse reaction is considered serious if in the view of the investigator or the sponsor, it results in any of the following:

- Death,
- A life-threatening adverse drug experience
- Inpatient hospitalization or prolongation of existing hospitalization
- Persistent or significant incapacity or substantial disruption of the ability to conduct normal life functions
- A congenital anomaly/birth defect.
- Important medical events that may not result in death, be life-threatening, or require hospitalization may be considered a serious adverse drug experience when, based upon appropriate medical judgment, they may jeopardize the patient or subject and may require medical or surgical intervention to prevent one of the outcomes listed in this definition.

6.1.6 Disability

A substantial disruption of a person’s ability to conduct normal life functions.

6.1.7 Life-threatening adverse drug experience

Any adverse event or suspected adverse reaction that places the patient or subject, in the view of the investigator or sponsor, at immediate risk of death from the reaction as it occurred, i.e., it does not include a reaction that had it occurred in a more severe form, might have caused death.

6.1.8 Protocol Deviation (NIH Definition)

Any change, divergence, or departure from the IRB-approved research protocol.

6.1.9 Non-compliance (NIH Definition)

The failure to comply with applicable NIH Human Research Protections Program (HRPP) policies, IRB requirements, or regulatory requirements for the protection of human research subjects.

6.1.10 Unanticipated Problem

Any incident, experience, or outcome that:

- Is unexpected in terms of nature, severity, or frequency in relation to
 - (a) the research risks that are described in the IRB-approved research protocol and informed consent document; Investigator's Brochure or other study documents, and
 - (b) the characteristics of the subject population being studied; **AND**
- Is related or possibly related to participation in the research; **AND**
- Suggests that the research places subjects or others at a *greater risk of harm* (including physical, psychological, economic, or social harm) than was previously known or recognized.

6.2 ASSESSING CAUSALITY

Investigators are required to assess whether there is a reasonable possibility that the study agent/s caused or contributed to an adverse event. The following general guidance may be used.

Yes: If the temporal relationship of the clinical event to the study agent/s administration makes a causal relationship possible, and other drugs, therapeutic interventions or underlying conditions do not provide a sufficient explanation for the observed event.

No: If the temporal relationship of the clinical event to the study agent/s administration makes a causal relationship unlikely, or other drugs, therapeutic interventions or underlying conditions provide a sufficient explanation for the observed event.

6.3 NCI-IRB AND CLINICAL DIRECTOR REPORTING

6.3.1 NCI-IRB and NCI CD Expedited Reporting of Unanticipated Problems and Deaths

The Lead PI will report on the NIH Problem Form to the NCI-IRB and NCI Clinical Director:

- All deaths, except deaths due to progressive disease
- All Protocol Deviations
- All Unanticipated Problems
- All non-compliance

Reports must be received within 7 days of PI awareness via iRIS.

6.3.2 NCI-IRB Requirements for PI Reporting at Continuing Review

The Lead PI will report to the NCI-IRB:

1. A summary of all protocol deviations in a tabular format to include the date the deviation occurred, a brief description of the deviation and any corrective action.
2. A summary of any instances of non-compliance
3. A tabular summary of the following adverse events:
 - All Grade 2 **unexpected** events that are possibly, probably or definitely related to the research;

- All Grade 3 and 4 events that are possibly, probably or definitely related to the research;
- All Grade 5 events regardless of attribution;
- All Serious Events regardless of attribution.

NOTE: Grade 1 events are not required to be reported.

6.3.3 Request for waiver from IRB reporting: Anticipated Protocol Deviations

Brief interruption and delay in the 28-day cycle may occasionally be required due to travel delays, airport closure, inclement weather, family responsibilities, security alerts and government holidays, etc. This can also extend to complications of disease not attributable to disease progression or protocol therapy. These delays will not be considered protocol deviations. We expect 1-2 anticipated delays per patient. However, any interruption more than 14 calendar days will not be permitted.

If the rate of these events exceeds the rate of more than 2 anticipated delays per patient, the events will be classified and reported as though they are unanticipated problems.

6.3.4 Multi-Institutional Guidelines

6.3.4.1 IRB Approvals

The Lead PI will provide the NCI IRB with a copy of the participating institution’s approved yearly continuing review. Registration will be halted at any participating institution in which a current continuing approval is not on file at the NCI IRB.

6.3.4.2 Amendments and Consents

The Lead PI will provide the NCI IRB with copies of all amendments, consents and approvals from each participating institution.

6.4 GUIDELINES FOR REPORTING SERIOUS ADVERSE EVENTS TO BTTC

What to Report?	When to Report?
1. All Deaths, except that due to progressive disease, occurring from the time the consent is signed through 30 days after the last day of active treatment	Within 1 working day (24 hours) from the time the research team becomes aware of event
2. Other Serious Unexpected Suspected Adverse Reactions (that did not result in death) occurring from the time the consent is signed through 30 days after the last day of active treatment	Within 5 working days from the time the research team becomes aware of event
3. All protocol deviations, non-compliance and unanticipated problems	Within 5 working days from the time the research team becomes aware of event

What to Report?	When to Report?

4. Pregnancy, although not itself a serious adverse event, should also be reported on a serious adverse event form and be followed up to determine outcome, including spontaneous or voluntary termination, details of birth, and the presence or absence of any birth defects or congenital abnormalities.
	
Within 5 working days from the time the research team becomes aware of event

The CCR problem report form will be used to submit adverse events to BTTC. See Appendix **13.6**.

Participating centers must also submit the report to their IRB in accordance with their institutional policies.

The BTTC Coordinating Center will maintain documentation of all Serious Adverse Events from each institution. The BTTC Coordinating Center will notify all investigators of any serious and unexpected adverse experiences that are possibly related to the study agent/s. The investigators are to file a copy with their protocol file and send a copy to their IRB according to their local IRB's policies and procedures.

6.5 REPORTING TO THE STUDY DRUG MANUFACTURERS

The BTTC Coordinating Center will forward all SAE reports to the NCI IRB via the Lead PI, FDA (when applicable), and Novartis and Bayer Pharmaceuticals.

The Lead Principal Investigator will report any SAEs, study drug exposure during pregnancy, and reports of misuse or abuse of study drug, including initial and follow up reports, to Novartis on a MedWatch form (including coversheet and Novartis Study Code found in M-CRADA) within 1 business day of becoming aware of such information.

The Lead Principal Investigator will forward to Novartis any findings that might alter the current benefit-risk profile of the study drug or that would be sufficient to consider changes in the study drug administration or in the overall conduct of the study within five calendar days of becoming aware of such information.

Bayer HealthCare Pharmaceuticals Inc.
[contact]
[contact]
Email: [contact]
Novartis Pharmaceuticals Corporation

Novartis Pharmaceutical U.S. DS&E Department

[contact]

If above Fax # is non-functional, send to:

[contact]

6.5.1 SAEs will be forwarded to Bayer/Onyx via the BTTC Coordinating Center in accordance with the following:

All serious adverse events should be reported to Bayer/Onyx within 24 hours. In the event of an SAE, the investigator should refer to the Pharmacovigilance section of the contract for reporting procedures. In brief:

The Lead PI may report serious adverse drug reactions (SADRs) using either:

An ADEERS form (Adverse Event Expedited Reporting System) available at <http://ctep.cancer.gov/reporting/adeers.html>

OR

A MedWatch form available at <http://www.fda.gov/medwatch/>

All reports shall be sent electronically to:

Electronic Mailbox: [contact]

[contact]

Address: Global Pharmacovigilance - USA

Mail only Bayer HealthCare Pharmaceuticals Inc.

[name]

[name]

Address: [name]

FDX or UPS only [name]

Reports for all Bayer products can also be phoned in via our Clinical Communications Dept:

[contact]

Occasionally BTTC may contact the reporter for additional information, clarification, or current status of the subject for whom an adverse event was reported.

6.5.2 Novartis Safety Information

The Lead PI shall report any other relevant/ important safety information to Novartis in the final study report and at such other periods as Novartis may request.

The Sponsor Principal Investigator shall ensure that at a minimum the form contains:

(a) Information on the person who contacted Sponsor (i.e., the initial reporter);

- (b) Information about the patient or clinical trial subject;
- (c) Details of the suspected Study Drug
- (d) Details on the safety events experienced by the patient

The Lead PI shall cooperate with all reasonable requests by Novartis to ensure that individual safety reports are sufficiently investigated, including requests to seek additional information relating to an individual safety reports or other relevant safety information.

The Lead PI shall perform SAE reconciliation between the Sponsor's Study database and an output of the Novartis Safety Database at the following time points:

- One year after First Patient First Visit and yearly thereafter
- At Last Patient Last Visit

The Lead PI will confirm that, for the period being reconciled, all information in the Sponsor's Study database that needed to be transferred to Novartis as per Novartis Annex, are contained in the output from the Novartis Safety Database. Where discrepancies are identified the Lead PI shall send/resend the information to Novartis DS&E as per the contact information in and using the supplied Novartis cover sheet.

Novartis U.S. Drug Safety and Epidemiology (DS&E) contact information for forwarding individual safety reports

- All reports of SAEs, drug exposure during pregnancy, study drug abuse or misuse Any Adverse Drug Reactions to Novartis products should be sent to U.S. DS&E at [contact]**
- The Novartis Coversheets must be attached to all SAE submissions
- SAE Submissions must reference the Novartis Study Code.
- Should the designated SAE Fax# be non-functional please send SAEs to the designated SAE mailbox: [contact])

The Lead PI shall provide the Novartis Medical contact listed in Novartis Annex with a written confirmation that the reconciliation was performed, the outcome of the reconciliation and documentation that, where discrepancies were identified, Novartis DS&E was informed (e.g. delivery confirmations).

6.6 GUIDELINES & PROCEDURES FOR REPORTING DEVIATIONS AND UNANTICIPATED PROBLEMS

Neither the FDA nor the ICH GCP guidelines define the terms "protocol violation" or "protocol deviation." The definition is often left to the Lead Institution IRB. Accordingly, since NCI, Center

for Cancer Research is the Coordinating Center and the Lead PI must adhere to those policies set by the NCI IRB, the definitions for unanticipated problem and protocol deviation as described by the NCI IRB will be applied for reporting purposes for all institutions participating in the NCI Center for Cancer Research Multi-center Project. Definitions are listed in section **6.1**.

Protocol Deviations or Unanticipated problems occurring at a participating institution will be submitted to that institution's own IRB in accordance with local policies and procedures. However, the participating institution must submit a report to the BTTC Coordinating Center even in instances where the local IRB does not require a report.

Deviations or Unanticipated Problems must be submitted to the BTTC Coordinating Center within 5 business calendar days after becoming aware of the event (if not reportable to the local IRB). When Deviations or Unanticipated Problems are reported to BTTC, but, the local IRB does not require a report, the report that is submitted to the BTTC Coordinating Center must be accompanied by a formal memo explaining the local policy and the rationale for not reporting the event to the local IRB.

Deviation or Unanticipated Problem Reports and any accompanying documentation (to include the local IRB acknowledgement of the event when applicable) are to be submitted to the BTTC Coordinating Center's Research Nurse, via [contact], or email using the problem report form in Appendix **13.6**

NCI Center for Cancer Research Coordinating Center: Upon receipt of the deviation/unanticipated problem report from the participating institution, the BTTC Coordinating Center will submit the report to the Lead Principal Investigator for review. Subsequently, the participating institution's IRB deviation/unanticipated problem report will be submitted to the NCI IRB for review.

6.7 DATA AND SAFETY MONITORING PLAN

6.7.1 Principal Investigator/Research Team

The clinical research team will have a teleconference every other week when patients are being actively treated on the trial to discuss each patient. Decisions about dose level enrollment and dose escalation if applicable will be made based on the toxicity data from prior patients.

All data will be collected in a timely manner and reviewed by the principal investigator or a lead associate investigator. Adverse events will be reported as required above. Any safety concerns, new information that might affect either the ethical and or scientific conduct of the trial, or protocol deviations will be immediately reported to the IRB using iRIS.

The principal investigator will review adverse event and response data on each patient to ensure safety and data accuracy. The principal investigator will personally conduct or supervise the investigation and provide appropriate delegation of responsibilities to other members of the research staff.

6.7.2 BTTC Coordinating Center Monitoring Plan

As the CCR is the coordinating center for this multi-site study, the CCR to maintain a monitoring program. The CCR's program allows for confirmation of: study data, specifically data that could affect the interpretation of primary study endpoints; adherence to the protocol, regulations, and SOPs; and human subjects protection. This is done through independent verification of study data with source documentation focusing on:

- Informed consent process
- Eligibility confirmation
- Drug administration and accountability
- Adverse events monitoring
- Response assessment.

The monitoring program also extends to multi-site research when the CCR is the coordinating center.

This trial will be monitored by personnel employed by an NCI contractor. Monitors are qualified by training and experience to monitor the progress of clinical trials. Personnel monitoring this study will not be affiliated in any way with the trial conduct.

6.7.3 Safety Monitoring Committee (SMC)

This protocol will require oversight from the Safety Monitoring Committee (SMC). Initial review will occur as soon as possible after the annual NCI-IRB continuing review date. Subsequently, each protocol will be reviewed as close to annually as the quarterly meeting schedule permits or more frequently as may be required by the SMC. For initial and subsequent reviews, protocols will not be reviewed if there is no accrual within the review period. Written outcome letters will be generated in response to the monitoring activities and submitted to the Principal investigator and Clinical Director or Deputy Clinical Director, CCR, NCI.

7.0 STATISTICAL CONSIDERATIONS

7.1 PHASE I COMPONENT

A Phase I design will be used where up to 6 patients will be treated at each dose combination. For each dose combination, three patients will be treated. If none show a DLT as defined in section 3.1.3, then the dose will be escalated for the next cohort of patients. If 2 or 3 have a DLT, then the previous dose (as defined in the cohort sequence above) is the maximum tolerated dose (MTD). If 1 of 3 patients has a DLT, then an additional 3 patients will be added to this dose. If 1 of 6 has a DLT, then the dose will be escalated. If 2 or more of 6 have a DLT, then the previous dose will be the MTD given that 6 patients have been treated in that dose. This 3+3 design has a 91% chance (70%, 17%) of dose escalating when the true toxicity rate for that dose is 10% (30%, 50%). It is expected that up to 6 dose combination will be observed, so that the expected sample size will range from 6 (if unacceptable toxicities are seen at the lowest doses) to 36 (if 6 patients per cohort are required for all 6 cohorts).

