The MTD will be based on the assessment of DLT during the first 28 days of treatment only (cycle-1), and will be defined as the dose at which fewer than one-third of patients experience a DLT to one of the study drugs. The MTD is the dose level at which 0/6 or 1/6 patients experience DLT with the next higher dose having at least 2/3 or 2/6 patients encountering DLT. Three patients will be treated at each dose level. If one dose limiting toxicity (DLTs) is encountered an additional 3 patients will be added to that dose level. If at any point two DLTs are encountered within a given dose level, then the MTD has been exceeded and three more patients are treated at the next lower dose (if only three patients were previously treated at that prior dose).

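### Section 7.1 gives a 70% chance of escalating at a true toxicity rate of 30%; the 3+3 rule as written gives 49%

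*Combined protocol and SAP*

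**What the plan says.** Section 7.1 states every branch of the Phase I rule:

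- Start: "For each dose combination, three patients will be treated".
- No DLT in three: "If none show a DLT as defined in section 3.1.3, then the dose will be escalated for the next cohort of patients".
- Two or three DLTs in three: "If 2 or 3 have a DLT, then the previous dose (as defined in the cohort sequence above) is the maximum tolerated dose (MTD").
- One DLT in three: "If 1 of 3 patients has a DLT, then an additional 3 patients will be added to this dose".
- One DLT in six: "If 1 of 6 has a DLT, then the dose will be escalated".
- Two or more DLTs in six: no escalation; the MTD is looked for at the dose below.

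The same section then summarises how the rule behaves: "This 3+3 design has a 91% chance (70%, 17%) of dose escalating when the true toxicity rate for that dose is 10% (30%, 50", where the closing bracket gives 50% as the third rate. Read in order, the pairs are 91% at 10%, 70% at 30% and 17% at 50%.

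Section 3.1.2 agrees on the stopping side: "If at any point two DLTs are encountered within a given dose level, then the MTD has been exceeded". It also sets the target, in that the MTD "will be defined as the dose at which fewer than one-third of patients experience a DLT to one of the study drugs".

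**The concern.** The sentence in Section 7.1 is the only place where the plan says how likely the Phase I rule is to escalate past a dose of given toxicity. These probabilities follow exactly from the rule, with no modelling choice, so they can be checked directly. A 70% chance of passing a dose with a 30% DLT rate looked too high for a design that stops at two DLTs.

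The 30% rate matters more than the other two because it lies just under the one-third limit in Section 3.1.2, which is where a reader wants to know how the rule behaves. As printed, the plan says the design would pass a 30%-toxic dose about seven times in ten. The Phase II dose comes out of this component, so a reader judging how that dose was selected would be working from a property the design does not have.

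**Working it through.** **Inputs (Section 7.1).** First cohort of 3. Escalate on 0/3. Add 3 patients on 1/3. Escalate on 1/6, which requires 0 DLTs among the added 3. Do not escalate on 2/3, 3/3, or 2 or more of 6. Let p be the true DLT rate at the dose, with patients independent.

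**Formula.**

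P(escalate) = P(0 of 3) + P(1 of 3) × P(0 of next 3) = (1−p)³ + 3p(1−p)² × (1−p)³ = (1−p)³ + 3p(1−p)⁵

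**The plan's three rates.**

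| True DLT rate | Calculation | Result | Section 7.1 states |
|---|---|---|---|
| 10% | 0.729 + 0.3 × 0.59049 | 0.9061 | 91% (agrees) |
| 30% | 0.343 + 0.9 × 0.16807 | 0.4943 | 70% (does not agree) |
| 50% | 0.125 + 1.5 × 0.03125 | 0.1719 | 17% (agrees) |

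The agreement at 10% and 50% indicates that this is the formula behind the sentence. At 30% the gap is 70.0 − 49.4 = 20.6 percentage points. A simulation of 2,000,000 cohorts gave 0.906, 0.494 and 0.172 at the three rates.

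**Could a different rule give all three figures?**

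| Rule | 10% | 30% | 50% |
|---|---|---|---|
| Stated in Section 7.1 | 91% | 70% | 17% |
| Escalate on 0/3 only | 72.9% | 34.3% | 12.5% |
| Escalate on at most 1/3, no expansion | 97.2% | 78.4% | 50.0% |
| Six at once, at most 1 DLT | 88.6% | 42.0% | 10.9% |
| Six at once, at most 2 DLTs | 98.4% | 74.4% | 34.4% |
| After 1/3, escalate on up to 2/6 | 96.5% | 68.9% | 31.3% |

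The last rule comes within about one point of 70% at 30%, but it contradicts the written stop at 2 or more of 6 and misses the other two stated figures by about 5 and 14 points. The stopping probability at 30% is 1 − 0.4943 = 0.5057, so a swap of stopping for escalating does not explain the figure either.

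**Where does the written rule give about 70%?** At p = 20%: 0.512 + 0.6 × 0.32768 = 0.7086. Solving for exactly 0.70 gives p ≈ 0.204. A figure calculated at 20% and printed against 30% is therefore a plausible origin, but the documents do not show it.

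**At the MTD limit.** At p = 1/3: 0.2963 + 0.1317 = 0.4280, so the rule escalates 42.8% of the time at exactly one-third.

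**The case against.** The strongest case on the other side is about weight, not arithmetic. Phase 1 is marked closed in the cohort table of Section 2.4. The Phase II regimen is fixed in Section 3.2.1 and matches dose level −1 of the Phase I dosing table. Escalation and the MTD were decided by DLT counts. The 6-to-36 sample size range in Section 7.1 comes from the number of cohorts and the patients per cohort. Phase II toxicity monitoring in Section 7.2 has its own rule and table. The error also makes the rule look less cautious than it is, so it hides no safety problem in conduct. And since the rule is printed in full beside the sentence, a careful reader can recompute the figure. All of this stands except the last point as a defence: a printed operating characteristic should not need recomputing.

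Two narrower points also stand without changing the result. Section 3.1.2 matches Section 7.1 on expansion after one DLT and on stopping at two, but does not itself state the step of escalating on 1 of 6. It also allows escalation to resume along a second dosing pathway after two DLTs at level 1 or level 2. Neither affects the figure, because the sentence in Section 7.1 concerns the chance of escalating from one dose with a given rate.

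Finally, the 20% explanation is an inference, and even there the rule gives 71%, not 70%. It should not decide how the sentence is corrected.

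**Conclusion.** The 70% is wrong. Under the rule as written, the chance of escalating past a dose with a true 30% DLT rate is 49.4%, about one in two; the plan overstates it by 20.6 percentage points. The figures at 10% and 50% are correct to rounding. The result assumes only the branches printed in Section 7.1 and independent patients with a common DLT rate at the dose. The origin of the error is not established, but 70% paired with 30% is wrong whatever the cause.

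The consequence is limited to the description of the Phase I design. No dose decision, sample size, stopping threshold or remaining analysis depends on the figure. It should nevertheless be corrected, because it misdescribes the rule close to the rate that defines the MTD.

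**What to change.** Amend the one sentence in Section 7.1. The fullest correction lists the escalation probabilities as 91%, 71%, 49% and 17% at true toxicity rates of 10%, 20%, 30% and 50%. The minimum correction changes 70% to 49% and leaves the rest. If the authors confirm from their own calculation that a 20% rate was intended, they could instead change 30% to 20% and 70% to 71%, but that drops the value nearest the one-third limit, so listing all four rates is better.

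The cost is one or two numbers in one sentence (one added pair for the fuller list). Conduct, sample size, decision thresholds and analysis are unchanged.
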